1. STUDY DESIGN

The study design was chosen according to the current standards required by ISO, GCP and according to national requirements.

- a. A Parallel-Arm, Statistician is blinded, RCT will be established;
- b. The RCT will be run as mono-center;
- c. A total of 40 subjects will be recruited to participate in the study. It is expected that all of 34 subjects will complete the study in total;
- d. Admission into the study will be via rolling admission (estimated recruitment time: 12 months);
- e. Each subject must have posterior monoedentulia (mandibular or maxillary) intercalated;
- f. Each subject will follow the following treatment protocol:
 1. Visit 1: (Screening)
 - a. Screening and entry into study.
 - b. Verification of the eligibility of each subject by performing intraoral radiography.
 - c. Explanation of the research protocol.
 - d. Consent secured.
 - e. Delivery of the medical request for CBCT (cone beam computed tomography) and for the antibiotic (Amoxicillin 1000mg 2cp/die every 12 hours for 6 days or Azithromycin 500mg 1cp/die every 24 hours for 6 days).
 2. When CBCT is ready the patient have to give it to the Principal Investigator to confirm the eligibility of each subject and to plan the surgery. Professional dental hygiene session is performed before surgery.
 3. Visit 2: (Treatment)
 - a. Assessment of antibiotic prophylaxis, locoregional anesthesia and opening of a thickness flap limited to the intervention area.
 - b. According to the list of randomization the patient will be allocated into one of the two arm of surgical treatment. Group A (control group): placement of the endosseous crestal implant through dedicated drills with 35N insertion torque and healing abutment. Group B (test group): placement of the endosseous subcrestal implant (2 mm under crestal bone) through dedicated drills with 35N insertion

torque and GFA (Gingival Former Abutment). Both group receive the same implant: TZero® (L= 9 mm, Ø 3,6 mm or L= 7,5 mm, Ø 4,3 mm) (Advan S.r.l. [name])

- c. Suture.
- d. Execution of intra-oral and post-operative X-Rays.

After 7 days of the surgery suture removal.

- 4. Visit 3: (after 3 months from visit 2) (Treatment)
 - a. Periodontal charting around the healing abutment or GFA (PD, BOP, PI) with calibrated periodontal probe.
 - b. Impression taking for prosthetic finalization.
- 5. Visit 4: (after a week from Visit 3: Baseline – T0): (Treatment)

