 - a. Prosthetic finalization and loading.
 - b. Periodontal charting around the new prosthetic crown (PD, BOP, PI, REC).
 - c. Take a standardized x- Ray (Bite Block).
- 6. Visit 5 (6 months from baseline – T1): (Follow-up)
 - a. Control.
 - b. Periodontal charting around the prosthetic crown (PD, BOP, PI, REC).
 - c. Take a standardized x- Ray (Bite Block).
 - d. Professional dental hygiene session.
- 7. Visit 6 (12 months from baseline – T2):
 - a. Control.
 - b. Periodontal charting around the prosthetic crown (PD, BOP, PI ,REC).
 - c. Take a standardized x- Ray (Bite Block).
 - d. Professional dental hygiene session.
- g. All treatments are made by the same clinician;
- h. Data collection:
 - Standardized X- Ray: control periapical radiographs is performed using a long-cone paralleling technique and an individual X-ray holder (bite block) to ensure reproducibility. Built thanks to impression material.
 - A calibrated periodontal probe (Click-Probe™ Kerr Dental) is used on six sites per tooth (mesio-buccal, buccal, disto-buccal, mesio-lingual, lingual and disto-lingual) with a standard probing force by the same clinician. Measurements are rounded to the nearest millimeter;

- j. Clinical and radiographical assessment data will be recorded via hard copy CRFs. CRFs will be submitted to a data entry staff member for entry into the statistical database. At the conclusion of the study, such statistical database will be submitted to the statistician for the preparation of the statistical analysis and the final study report.
- k. Prosthetic finalization is given to the dental laboratory.

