2. TREATMENTS

Implant kit, implants and every component will be delivered to the study center prior study start by Advan S.r.l. [name]:

- Surgical Kit PRO: GKC13
- Set countersink GFA: GKM10
- Kit stop drills: GST11
- Implant: TZero - T3609 (D3,6 L9,0) - T4307 (D4,3 L7,5)
- GFA: 04GFX03 (D4,0 H3,5) - 04GFX04 (D4,0 H4,5) - 04GFX05 (D4,0 H5,5)
- component GFA: 01GFT01 (healing stopper H1) - 01GFT03 (healing stopper H3) -01GFT05 (healing stopper H5) - 01TGF10 (transfer pick-up) - 01AGF10 (analogo GFA) -01CGF40 (moncone calcinabile con base in cobalto-cromo)
- for control group: 05OMG12 (healing abutment H2) - 05OMG13 (healing abutment H3) - 05OMG14 (healing abutment H4) - 01OTR10 (transfer pick-up) - 41CCN40 (moncone calcinabile con base in cobalto-cromo)

Radiographically Analysis

Specification of software analysis

Peri-apical x-ray examinations will be performed using phosphor image plates (FONA™ Dental Image Plates) and then acquired through a digital scanner device (FONA ScaNeo™).

All radiographical images will be later analyzed by the same external examiner, which will measure marginal bone level parameter (MBL) around placed endosseous implants using an image analysis software (ImageJ™).

In particular bone levels will be determined, both mesially and distally the dental implant, using the “Measure” function of the software, which records the distance between the most apical bone point and the most coronal bone point in 0.3 mm range from the implant.

Measurements will be all recorded to allow the observation of bone level changes over time.

Concomitant Therapy

A necessary concomitant medication or therapy is permitted as long as it is not excluded in the exclusion criteria. Every medication has to be reported in the CRF (Appendix 1) and in the Concomitant Medication form (Appendix 2). All changes during the study are to be reported in the CRF. Usage of prohibited therapy will lead to the exclusion of the subject.

Blinding and Randomization

Blinding:

The statistician and the patient will be blinded to the group identification. The operator will know the treatment allocation. Knowledge of the randomization list will be limited to the persons responsible for creation of the randomization list, provider of randomization numbers to study site, and delivery of the test/control treatment until the last subject (i.e. final examination of the last subject), quality control and verification of the CRFs is completed.

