Randomization and allocation concealment:

The randomization of the study protocols will be performed by a staff member who is not further involved in this study. This will be done based on a computer-generated table (using R package *randomizeR*) that links each patient to one of the treatment groups. Treatment allocation will be delivered in sealed envelopes.

Implementation: The Principal Investigator will be informed immediately of Serious Adverse Events (SAEs), regardless of the causality relationship between the administration of the investigational treatment and the SAE.

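### The blinding rule, read naturally, lets the treating clinician know the randomization list while recruitment is open, which contradicts the sealed-envelope concealment

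*Combined protocol and SAP*

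**What the plan says.** Four parts of the protocol bear on who can know an allocation, and when.

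- **Section 2, Blinding.** The operator's position is stated first: "The operator will know the treatment allocation". The next sentence concerns the list itself. It limits knowledge of the list to those who create it, then adds "provider of randomization numbers to study site, and delivery of the test/control treatment until the last subject", and runs on to that subject's final examination and verification of the CRFs.
- **Section 2, Randomization and allocation concealment.** A staff member with no other part in the study performs the randomization from a computer-generated table. "Treatment allocation will be delivered in sealed envelopes". The text does not say who holds, hands over or opens the envelopes, or whether they are opaque or numbered.
- **Section 1, Study Design.** Admission is rolling, over an estimated 12 months. After the CBCT, "the patient have to give it to the Principal Investigator to confirm the eligibility of each subject and to plan the surgery". At Visit 2, once the flap is open, "According to the list of randomization the patient will be allocated into one of the two arm of surgical treatment". Item g adds: "All treatments are made by the same clinician".
- **Section 3, Procedure.** A dental examiner screens patients, and those identified for treatment are randomized by a randomization table. Envelopes are not mentioned here or at Visit 2.

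**The concern.** Knowing the arm of the patient on the table is unavoidable in this surgery and is not a defect. Knowing the arms of patients not yet entered is a different matter, and the list contains exactly that. If the one treating clinician may hold the list during recruitment, a sealed envelope no longer hides the next allocation from that person.

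Several steps before allocation involve judgement: reading the CBCT, deciding whether medication or disease could interfere with healing, and planning the surgery. Section 9 also allows case-by-case eligibility waivers, and Study Population allows subjects excluded for major deviations to be replaced. Someone who knew the next arm and had influence over any of these steps could defer, rebook or decline a patient accordingly. The result would be selection bias in the comparison of marginal bone level (MBL) change. The planned t-test and GEE name no covariates and could not be relied on to remove it.

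**Working it through.** **1. Does the access rule cover the operator?** The sentence names three functions: creating the list, providing randomization numbers to the site, and delivering the test or control treatment. Handing allocations to the site is already the second function. The manufacturer supplies kits, implants and components before the study starts, which needs no list. Treating patients is the most natural meaning left for the third function, and Section 1 item g assigns all treatment to one clinician.

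**2. Does the rule cover the recruitment period?** Yes. It runs to the final examination of the last subject and CRF verification, so it spans the estimated 12 months of rolling admission.

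**3. Is it only about the current patient's arm?** No. The preceding sentence already deals with the operator's knowledge of the allocation. This one concerns the list.

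**4. Do the operational steps resolve the conflict?** No. Visit 2 and Section 3 refer to the list or table, not to an envelope, and no passage denies the operator the list.

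**5. The plan's own figures.** Inputs from Section 4: SD 0.5 mm, difference 0.5 mm, power at least 80%, alpha 5%, 15% drop-out. Two-sided testing is assumed, because sidedness is not stated.

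- Normal approximation: n per arm = 2(1.960 + 0.842)² × (0.5/0.5)² = 15.7, rounded up to 16, or 32 in total.
- Exact noncentral-t power: 0.781 at 16 per arm and 0.807 at 17 per arm. So 34 is the correct t-test answer.
- Drop-out: 34/0.85 = 40.

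The stated sample size reproduces. Concealment does not enter any of these formulas, so N, power and nominal alpha do not change.

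**6. Hypothetical bias.** Nothing in this step beyond the SD, the design difference and 17 per arm comes from the documents. Assume that the 20% of candidates with the worst prognosis are kept out of one arm and that the other arm's mix is unchanged.

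- Shift in mean prognosis = φ(0.8416)/0.8 = 0.280/0.8 = 0.35 SD.
- Bias in MBL change = 0.35 × 0.5 mm × r, where r is the assumed correlation of prognosis with MBL change.

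| r | Bias (mm) | Share of 0.5 mm |
|---|---|---|
| 1.0 | 0.175 | 35% |
| 0.5 | 0.0875 | 17.5% |
| 0.3 | 0.0525 | 10.5% |

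The first row requires perfect prediction of bone change before surgery and is an upper limit for this steering rate.

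**7. What a given bias would do to the test.** With no true effect, SD 0.5 mm and 17 per arm, the standard error is 0.5 × √(2/17) = 0.171 mm. The two-sided 5% t-test would then reject as follows:

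| Assumed bias (mm) | Probability of rejection |
|---|---|
| 0 | 5.0% |
| 0.05 | 5.9% |
| 0.10 | 8.7% |
| 0.15 | 13.6% |
| 0.20 | 20.5% |

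**The case against.** The point depends on how one badly built sentence is read. Elsewhere the protocol uses deliver and delivery for handing things over: components, a medical request, allocations, the final report. Surgery is described as placement, or as treatments that are made. The surgeon is called the operator and has a separate sentence, which would be largely redundant if the next one already granted the whole list. The sentence is framed as a limit on access, and the concealment paragraph does provide an independent randomizer and sealed envelopes. Allocating by the list at Visit 2 may be shorthand for envelopes prepared from it. Section 1 also places allocation after consent, CBCT eligibility and opening of the flap.

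Much of this stands. The alternative reading of delivery is possible, which is why confidence is medium. It is the weaker reading, because the functions it would cover are either already listed or need no list. The sequence at Visit 2 is sound, but it does not protect against someone who already knows the list.

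A reader might infer that the envelopes conceal nothing. The documents do not support that: the envelopes would work if the operator is never in fact given the list, and they could still conceal from a screener without access. A reader might also infer that the operator decides who enters. The text gives screening to a dental examiner and confirmation of eligibility to the Principal Investigator, and does not say whether either is the operator. Nor does it say that the uninvolved staff member hands over the envelopes, only that this person performs the randomization.

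**Conclusion.** The concern holds as a contradiction between two parts of Section 2. The blinding rule, on its natural reading, permits the single treating clinician to know pending allocations throughout recruitment, while the concealment paragraph depends on that not happening. It is a stated access rule, not merely a missing detail. The route from it to selective enrolment is possible but not established.

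The documents give no basis for a bias estimate. The range of 0.05 to 0.175 mm rests on an assumed 20% steering rate and assumed correlations of 0.3 to 1.0, and only illustrates what could follow. A reader might conclude that randomization no longer supports a causal reading of the result. That goes too far, because permission to see the list is not evidence that anyone will see it or act on it. Severity is should-fix, with medium confidence.

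**What to change.** 1. **Section 2, Blinding.** Remove treatment delivery from the functions that may know the list. State that the operator, and anyone who screens patients, confirms eligibility or books surgery, does not see it and learns each allocation only when that patient's envelope is opened.
2. **Section 1, Visit 2, and Section 3, Treatment.** Replace allocation by the list or table with opening the next sequentially numbered, opaque, sealed envelope. Keep this at the point in Visit 2 where allocation already stands, after eligibility and entry are final and recorded.
3. **Section 2, Randomization and allocation concealment.** State that the uninvolved staff member keeps the list and prepares the envelopes.

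The cost is wording in a few places. The envelopes and the uninvolved staff member are already planned, and no visits, staff or patients are added. The change should be made before the first patient is randomized, because concealment lost during recruitment cannot be restored afterwards.

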3. PROCEDURE

Screening and Selection of Subjects

Patients visiting the U.O. Odontostomatology of ASST Spedali Civili of Brescia will be asked to participate in this study. Subjects will report to the clinical facility and be screened by the dental examiner to identify those subjects who meet the inclusion/exclusion characteristics. The findings of this initial screening procedure will be recorded on the CRF. Subjects who meet the inclusion/exclusion characteristics and sign an Informed Consent Form will be entered into the study.

Baseline Oral Soft and Hard Tissue Assessment

All subjects will receive an evaluation of their oral soft and hard tissues. This examination will include an evaluation of the soft and hard palate, gingival mucosa, buccal mucosa, mucogingival fold areas, tongue, sublingual and submandibular areas and the tonsillar and pharyngeal areas. The results of this evaluation will be recorded on the CRF.

CBCT

All patients receiving a CBCT to confirm the eligibility of each subject and to plan the surgery at Complex Operative Unit of Diagnostic Radiology 2.

Treatment

Patients who have been identified for treatment receive an implant placement and prosthetic finalization will be randomized according to a randomization table generated.

Clinical Periodontal Evaluation

All patients receiving treatment will be evaluated by the dental examiner for the following assessments (see Study Flow Chart):

- Full Mouth Plaque Score (PI);
- Periodontal Inflammation (BOP);
- Probing Pocket Depth (PD);
- Recession (REC);

All parameters will be recorded in the CRF.

Radiographically Evaluation

All patients receiving control reproducible periapical radiographs for evaluation of MBL (mesial and distal) (see Study Flow Chart)

All parameters will be recorded in the CRF.

Follow up

Following completion implant placement and prosthetic finalization, the study start. Radiographically and clinical evaluation will be done at baseline (T0), 6 and 12 months (T1 and T2) in the test and control site. At 6 and 12 months a dental hygiene session and OHI will be done.

Study Flow Chart

Study phase	Enrolment	Treatment	Treatment	Treatment	Follow-up	Follow-up
Study visit	Visit 1	Visit 2	Visit 3	Visit 4 (T0)	Visit 5 (T1)	Visit 6 (T2)
Study Time	- X days	0	3 months	3 months and 1 week	6 months from visit 4	12 months from visit 4
Selection criteria	+					
Informed consent	+					
Demographics, ethnics	+					
General health status	+	+	+	+	+	+
Medical & dental history	+					
Concomitant therapy/treatment	+	+	+	+	+	+
Safety (adverse events and serious adverse events)			+	+	+	+
Data collection (PD,REC, BOP, PI)	+			+	+	+
X- Rays and CBCT	+	+	+	+	+	+
Randomization		+				
Professional Oral Hygiene session	+				+	+
Prosthetic Finalization			+	+		
Implant Placement		+				
GFA or healing abutment		+				

4. STATISTICAL ANALYSIS

Sample size determination

Sample size was compute assuming a two parallel groups design with balanced groups and an independent sample t-test. We assumed a single implant and a single measurement for patient, a standard deviation of 0.5 mm and an average difference of at least 0.5mm. A total sample size of 34 patients will provide a power of at least 80% at a 5% significance level. Assuming a 15% drop-out , the total sample size will be N=40 patients.

Statistical Analysis

Data will be described using standard statistics such as, mean, median standard deviation and IQR for quantitative variable, and counts and percentages for qualitative variables.

Variation in MBL will be modelled using both a simple t-test for independent samples (after averaging values within patients) as well as a multilevel model using GEE (Generalised Estimating Equations) on individual site measurements and accounting for within subject correlation.

Secondary continuous outcomes will be modelled using GEE with ad hoc error distribution according to outcome (Gaussian for PPD, CAL, REC, binomial for BOP).

Results will be expressed as estimates and relative 95% confidence intervals. A significant level of 5% will be used for all the comparisons and all analysis will be performed using R (version 3.6.3 or higher).

Evaluation of Safety

The following safety variables will be used for the evaluation of safety:

- Adverse events (AE);
- Adverse reactions (AR).

The total number of AEs and the total number of AEs at least possibly related to the study treatment, as well as the total number of patients affected by at least one adverse event will be calculated per treatment group.

The type of AE classified by organ system (according to MedDRA terminology) will be tabulated. Serious and/or unanticipated adverse events and AEs resulting in discontinuation or reduction/withdrawal of the study treatment will be presented separately.

Safety analysis set

Safety summaries will be based on the safety analysis set which will consist of all patients who received the test/control treatment.

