- Good oral health (no decay, periapical or periodontal lesions, PI and BOP < 25%).
- Patient with posterior monoedentulia:
 - at least 5 months,
 - mandibular or maxillary,
 - intercalated (distance between teeth more than 7.5 mm),
 - at least 11 mm of height residual bone (from bone crest to maxillary sinus or inferior alveolar nerve),
 - at least 5 mm of bone width (buccal – palatal/lingual).
- Availability for the 12-month duration of the study for an assigned subject.

Exclusion Characteristics

- Not willing to follow the agreed protocol.
- Presence of orthodontic appliances.
- Smokers more than 10 cigarettes per day.
- Chronic obstructive pulmonary disease and asthma.
- Tumors or significant pathology of the soft or hard tissues of the oral cavity.
- Current radiotherapy or chemotherapy.
- Pregnant or lactating women.
- Parafunctions like bruxism.
- Previous interventions to increase bone thickness in the implant area.
- Current or past assumption of medications that may influence surgical therapy and/or interfere with healing following surgical treatment.
- Systemic diseases that constitute a contraindication to surgical therapy and/or interfere with healing following surgical treatment.

A written informed consent will be obtained from each included patient after explanation of the risks and benefits of participating to this study. No change in the trial design will be made after approval of the Ethical Committee.

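### Jaw is known before randomisation but enters neither the allocation list nor the named MBL analyses, so neither equal arms nor balance on jaw is secured; this costs precision, not validity

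*Combined protocol and SAP*

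**What the plan says.** **Eligibility.** Section 1 (Study Design) states: "Each subject must have posterior monoedentulia (mandibular or maxillary) intercalated". No quota or target mix is given. The Inclusion Characteristics measure bone height to a different structure in each jaw: "at least 11 mm of height residual bone (from bone crest to maxillary sinus or inferior alveolar nerve").

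**Timing.** The site is radiographed at Visit 1, then CBCT follows: "When CBCT is ready the patient have to give it to the Principal Investigator to confirm the eligibility of each subject". Randomisation is at Visit 2 (section 1; Study Flow Chart in section 3). Jaw is therefore fixed and documented before allocation.

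**Allocation.** Under Randomization and allocation concealment (section 2), the list is a "computer-generated table (using R package *randomizeR*) that links each patient to one of the treatment groups", delivered in sealed envelopes. No block, stratum or allocation ratio is mentioned.

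**Sample size.** Section 4 computes power "assuming a two parallel groups design with balanced groups" and an independent-samples t-test, with SD 0.5 mm, difference 0.5 mm, 5% significance and 80% power. This gives 34 evaluable patients, and 40 after 15% drop-out.

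**Analysis.** Section 4 continues: "Variation in MBL will be modelled using both a simple t-test for independent samples (after averaging values within patients"), together with a GEE on individual site measurements. No covariate is named for either, and no jaw-specific or jaw-adjusted analysis is planned.

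**The concern.** With about 17 patients per arm, chance can leave the arms unequal in size or in jaw mix. If MBL change differs between jaws, an unadjusted comparison carries that difference as extra residual variance, and in any single trial an uneven jaw split shifts the estimate. A t-test cannot take jaw into account.

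The calculation has little slack: 17 per arm is the smallest arm size that reaches 80% power on the stated inputs, and that figure needs equal arms. The allocation text does not say how equality will be achieved. A better list cannot be produced once patients have been allocated, and a covariate chosen after the data are seen is less credible than one named beforehand.

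**Working it through.** **Inputs.** From section 4: difference δ = 0.5 mm, SD σ = 0.5 mm, α = 5%, 34 evaluable. Sidedness is not stated; two-sided reproduces the plan's figure. Not in the documents, and therefore assumed: the jaw mix, and the difference between jaws in mean MBL change (d_J, taken from 0 to 0.5 mm).

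**1. The plan's own figure.** Non-central t with λ = δ / (σ√(1/n₁ + 1/n₂)).
- 17/17: λ = 0.5 / (0.5 × √(2/17)) = 2.915, df 32, power 80.7%.
- 16/16: λ = 2.828, df 30, power 78.1%.
- So 34 is right, and 34/0.85 = 40.

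**2. Unequal arms.** The same formula with n₁ + n₂ = 34 gives 80.2% at 19/15, 79.5% at 20/14 and 77.1% at 22/12. If allocation were unrestricted, n₁ would be binomial(34, 0.5): 39% of splits would be 20/14 or worse, and power averaged over all splits would be 79.5%.

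**3. Imbalance on jaw.** With 17 per arm and K maxillary sites among 34, the number in one arm is hypergeometric.
- K = 17: the arms differ by 3 or more patients (18 points) in 49% of trials, and by 20 points or more in 17%. The count difference must be odd here, so 20 points or more means at least 5 patients, or 29 points.
- K = 12: the arms differ by 20 points or more (at least 4 patients, 24 points) in 28%.
- Shift in the unadjusted estimate = difference in share × d_J. For 5/17 this is 0.09 mm at d_J = 0.3 mm and 0.15 mm at 0.5 mm, against a target of 0.5 mm.

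**4. Gain from stratifying and adjusting.** At a 50:50 mix with total SD held at 0.5 mm, jaw explains R² = (d_J²/4)/0.25 = d_J² of the variance (d_J in mm). The residual SD is 0.5√(1 − R²) with df 31. The right-hand column is from simulation (40,000 replicates).

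| d_J (mm) | R² | Stratified and adjusted | Adjusted, not stratified |
|---|---|---|---|
| 0 | 0% | 80.6% | 79.4% |
| 0.1 | 1% | 81.0% | 79.8% |
| 0.2 | 4% | 82.2% | 81.0% |
| 0.3 | 9% | 84.1% | 82.6% |
| 0.5 | 25% | 90.3% | 89.6% |

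The comparator is 80.7% throughout (80.3% to 80.9% when the planned t-test is simulated).

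**5. Cost if jaw is irrelevant.** With both changes: 80.7 − 80.6 = 0.1 point. With adjustment alone: 80.86 − 79.41 = 1.45 points by simulation, and 80.70 − 79.36 = 1.34 points by averaging the non-central t power over the hypergeometric splits. Call it 1.4.

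**6. Validity.** Simulated type I error of the planned t-test without stratification is 5.0% to 5.2% for d_J from 0.2 to 0.5 mm. Stratifying but keeping the unadjusted t-test makes it conservative: 4.0% at 0.3 mm and 2.8% at 0.5 mm.

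**7. If 0.5 mm is the within-jaw SD.** The total SD is then √(0.25 + d_J²/4), and the planned t-test has about 79%, 77% and 72% power at d_J = 0.2, 0.3 and 0.5 mm. The documents do not say which SD is meant.

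**The case against.** The strongest reply is that nothing in the documents says jaw predicts MBL change. Jaw appears only in eligibility, and the Introduction discusses bone loss without separating the jaws. The larger gains rest on large assumed effects; 0.5 mm equals the whole target difference. At 0.1 to 0.2 mm the gain is 0.3 to 1.5 points. This stands, and it limits the weight of the point.

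A reader might infer more than the text supports:
- *That the t-test is biased or invalid.* Randomisation keeps it unbiased on average, with type I error near 5%.
- *That the list is unrestricted.* The section is silent on method, and naming a software package does not identify the procedure. The 79.5% average is conditional on unrestricted allocation, and a 20/14 split costs only 1.2 points (80.7 − 79.5).
- *That the t-test is the sole primary analysis, or that the GEE excludes jaw.* Section 4 names both methods without saying which decides, and the GEE's covariates are simply unspecified.
- *That smoking belongs in the model too.* Smokers of up to 10 cigarettes a day are eligible, but no evidence on the size of any effect is available here, so it is not proposed.

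**Conclusion.** The point holds as a cheap improvement in precision and protection against chance imbalance; the sample size is not in error. Without any assumption about jaw, the plan does not say how the equal arms behind its power figure will be obtained, and it has only 0.7 points of margin over 80%.

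With the assumed 50:50 mix and total SD 0.5 mm, the paired change moves power from 80.7% to between 80.6% (no jaw effect) and 90.3% (0.5 mm), with 84.1% at 0.3 mm. The imbalance figure that matches this mix is 17%; the 28% figure belongs to 12 maxillary sites among 34 and should not be set beside these gains. How much is really gained depends on a jaw effect that the documents do not give.

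**What to change.** Make both changes together, before the first patient is randomised.

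1. **Section 2, Randomization and allocation concealment:** state that the list is generated 1:1 in permuted blocks of randomly varied size, stratified by jaw. Varied sizes matter because the operator knows each allocation. Incomplete blocks in two strata mean that the totals will be near 1:1 but 20:20 is not guaranteed, and drop-out can disturb balance among completers.
2. **Section 4, Statistical Analysis:** replace the simple t-test by a linear model of patient-mean MBL change on arm and jaw, testing the arm coefficient. Put the same jaw term in the GEE. Keep the unadjusted difference as a supportive result.

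MBL at T0 should not take the place of jaw as the covariate, because it is measured about three months after the allocated surgery.

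**Cost.** No extra patients, visits or measurements. If jaw is irrelevant, about 0.1 point of power is lost with both changes, or about 1.4 points if jaw is adjusted for without stratifying. Stratifying without adjusting makes the test conservative. If ethics approval has already been given, an amendment under section 9 is needed, and the statement closing the Study Population section, which rules out design changes after approval, must be reconciled with it.
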